1.10.3. Follow-up period (outpatient, day 11 – day 196)

Participants will return to the ICRRU or ICRF on days 14 and 28 post infection for assessment and sampling, including bronchoscopy on day 28. During the 6 months after challenge, subjects will be asked to report all episodes of upper respiratory tract symptoms. If an episode of natural infection occurs, the subject will be asked to re-attend for blood and upper respiratory tract samples to be collected. After 6 months, subjects will be asked to return for further samples to be taken, including bronchoscopy if subject has been included for this. A second dose of RSV administered a week later in the RSV arm only. Further samples will be collected at the peak of the secondary response 7 days post-infection. We will not do every test on every visit as can be seen from Table 2. The total study period for each subject is 210 in the RSV arm and 42 in the influenza arm.

STUDY PROCEDURES

A variety of procedures are carried out during the study period. The frequency and timing of these procedures are shown in above. For the screening, and days -14, 14, 28 and 196 visits, procedures will take place in the procedures room on ICRRU or ICRF; for days 0 to 10 and 168 to 179 subjects in the RSV and influenza arms of the study will reside in the confinement facility and procedures will take place there (with the possible exception of virus inoculation and bronchoscopy).

1.11. Virus Inoculation

GMP influenza A/California/04/2009-like (H1N1); influenza A/Belgium/4217/2015 (H3N2); or RSV Memphis 37 virus strains will be used for experimental infection of volunteers. On the day of inoculation (day 0 and day 168), RSV or influenza virus stock will be defrosted from its storage in the freezer. Subjects will be inoculated with intra-nasal drops on a single occasion with diluted inoculum at a given dose divided equally between the two nostrils. This will be done slowly with sufficient interval between each inoculation (2-3 minutes) to ensure maximum contact time between with the nasal and pharyngeal mucosa. Subjects will be asked not to swallow during the procedure to ensure maximal pharyngeal contact. The inoculation procedure will be performed using a ventilated body box, allocated isolation bay or negative pressure room in the ICRRU or ICRF. Inoculations using intranasal drops will be done using a 1mL pipette with subjects supine. Following inoculation, advice regarding hand hygiene will be given and subjects will be provided with alcohol hand gel and face-masks to reduce spread of virus in the home environment.

1.12. Swabs for microbial analysis

1.12.1. Throat swab

A sterile dry cotton-headed swab is used to obtain samples from the pharynx for bacterial 16S gene analysis. This is performed with the subject sitting. Ensure adequate lighting and use a tongue depressor if required. Remove the swab from the container carefully to ensure the tip is not contaminated, and swab the dorsal aspect of the pharynx and soft palate, avoiding the tongue. Some subjects may experience a strong gag reflex. Obtain two samples; place one used swab into a dry container and freeze at -80°C prior to analysis and another into bacteriology culture medium.

1.12.2. Stool swab

Sterile dry cotton-headed swabs will be used to obtain stool samples for bacterial 16S gene analysis. These will be collected by the subject from the toilet paper after opening their bowels.

Procedure:

- Remove the swab from the collection tube by holding it firmly by the red cap. **DO NOT TOUCH THE COTTON PART WITH YOUR BARE HANDS!**
- Collect a small amount of fecal material by rubbing the cotton tip of the swab on a faecal sample: a piece of used bathroom tissue is the best material possible. A small amount is enough: it should cover half of the cotton tip. Do not try to collect too much biomass.
- Replace the swab in the collection tube and close it by pushing firmly on the cap.
- Store the swab at -80°C within 48h. If it is not possible to store at -80°C, store the sample at 4°C until transfer into a cryogenic environment.

1.13. Nasal sampling procedures

All nasal procedures will be performed in the order below **prior** to the bronchoscopy to avoid contamination by the local anaesthetic gel and bronchoscope introduced into the nose.

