1.9. Withdrawal criteria

Any subjects can withdraw from the study at any time if they wish to. Subjects can also be removed from the study if an investigator feels this is necessary or appropriate. Subjects will be closely monitored throughout by the study doctor. This is defined further in the section on 'Serious Adverse Events'.

STUDY DESIGN**Figure 1: Subject allocation**
Day 0**Table 1: Study procedures (Screening to day 9)**

Procedures	DAY (relative to viral inoculation)												
	Screen	-14	0	1	2	3	4	5	6	7	8	9	
Consent	X												
Physical Examination	X	X	X							X			
Lung Function Testing – FEV ₁ , peak flow & breath tests	X	X	X	X	X	X	X	X	X	X	X	X	X
Screening blood tests	40												
Blood - serum			5										
Blood for HLA typing	5												
Blood - PBMCs (mls)			40										
Blood – plasma (mls)		X	6 x 2	6 x 2	6 x 2	6 x 2	6 x 2	6 x 2	6 x 2	6 x 2	6	6	
Blood – RNA (mls)			7.5 x 2	7.5 x 2	7.5 x 2	7.5 x 2	7.5 x 2	7.5 x 2	7.5 x 2	7.5 x 2	7.5	7.5	
Throat & stool swabs	X	X		X	X	X	X	X	X	X	X	X	X
Nasal lavage (daily)	X	X	X	X	X	X	X	X	X	X	X	X	X
Nasosorption using SAM (right nostril)	X	X		X	X	X	X	X	X	X	X	X	X
Nasal scrape (Rhinopro®)	X	X		X	X	X				X			
Bronchoscopy: Bronchosorption using SAM (4) Bronchial biopsy (6) Bronchial brush (4) Bronchoalveolar lavage (BAL)		X											
Virus inoculation			X										
Review symptom diaries daily	X	X	X	X	X	X	X	X	X	X	X	X	X
Collect symptom diaries													
Urine pregnancy test	X		X										

Table 2: Study procedures (day 10 to day 196)

Procedures	DAY (relative to viral inoculation)							
	10	14	28	161	168	178	182	196
Consent				X				
Physical Examination	X	X	X	X	X	X	X	X
Lung Function Testing – FEV ₁ , peak flow & breath tests	X	X	X	X	X	X		
Screening blood tests								
Blood - serum			5		5		5	5
Blood for HLA typing								
Blood - PBMCs (mls)	60		40	20	40	60	60	60
Blood – plasma (mls)	6	6	6					
Blood – RNA (mls)	7.5	7.5	7.5	7.5	7.5	7.5	7.5	7.5
Throat & stool swabs	X	X	X		X	X	X	X
Nasal lavage (daily)	X	X	X	X		X		
Nasosorption using SAM (right nostril)	X	X	X		X	X	X	X
Nasal scrape (Rhinopro®)	X				X	X	X	X
Bronchoscopy: Bronchosorption using SAM (4) Bronchial biopsy (6) Bronchial brush (4) Bronchoalveolar lavage (BAL)	X		X				X	
Virus inoculation					X			
Review symptom diaries daily	X	X			X	X	X	X
Collect symptom diaries		X					X	
Urine pregnancy test			X	X				

SAM = synthetic absorptive matrix

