1.13.1. Nasal scrape using Rhinopro®

Rhinopro® curettes will be used to obtain a sample of nasal epithelial cells from each nostril. This is a painless procedure and will not require local anaesthetic. The following technique is used:

The subject should be sat comfortably, ideally with their head fixed, looking forward, while their chin rests on a support (if available)

Tear bag and remove the flexible plastic Rhinopro® without contaminating the scoop end

Place a speculum in the nose to keep the cavity open and employ good lighting

Under direct visual inspection, insert the cupped probe onto the surface of the mid-inferior portion of the inferior turbinate. Note: Avoid the anterior bulb.

The Rhinopro® should be 3cm up the nose; the floor of the nostril can be used to rest on

Have the cup of the Rhinopro® at the correct angle

Gently press the cupped tip on mucosal surface and move out and in of nostril 3mm up to 3 times

Note that this area has limited sensitivity and the subject should not find this procedure painful, although a nasolacrimal reaction usually occurs

The cell harvest is epithelial cells, goblet cells and mast cells. It does not contain deeper layers of the mucosa. The sample obtained should be placed immediately into a tube containing RNA Cell Protect® (Qiagen) or Trizol and frozen at -80°C for storage prior to analysis.

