1.13.2. Nasosorption

Up to four strips of SAM will be used (2 per nostril, one after the other) for 2 minutes to obtain repeated samples of neat nasal ELF. This is a painless minimally invasive procedure that will not require any local anaesthetic. Following sampling, SAM will be placed in a 1mL microfuge spin filter tube containing 250µL of elution buffer (PBS/1% bovine serum albumin/0.05% azide/0.05% Triton®). Further details are given in the SOP Human Sampling Procedures for Challenge Study.

The SAM will be transported on ice to the laboratory.

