1.13.3. Nasal Lavage

Nasal lavage is performed using the following technique:

- 5mL of 0.9% saline is introduced into each nostril using a syringe attached to a nasal olive with the subject sitting with the head tilted forward
- The saline is then washed in and out of the nose approximately 10 times by alternately withdrawing and advancing the plunger of the syringe while the subject maintains a tight seal between the nasal olive and the nostril; the aim is to recover ~80% of the saline from the nose
- The fluid is then aliquotted into sterile microfuge tubes and centrifuged for analysis of cells

Lavage fluid will later be analysed to quantify the degree of RSV or influenza shedding. Multiplex PCR will be performed on the pre-inoculation lavage and post-inoculation lavage collected during the study to exclude the presence of other respiratory viruses. Supernatants will be frozen and stored at -80°C. Further details are given in the SOP Human Sampling Procedures for Challenge Study.

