Based on pilot data from de Bree et al., we calculate that a sample size of 16 in each arm will be sufficient to find a difference of 1.4 between epitope-specific T cell counts in blood and lung, with 80% power using a 2-sided unpaired t-test with 5% significance level (where the variability in each group is 1.3). T cell numbers will be compared between RSV and influenza using an unpaired t-test (if normality of the T cell distribution, or its transformation, is satisfactory as assessed by histogram with q-qplot and Shapiro-Wilks test) or a Mann-Whitney test (if normality is not satisfactory). We will perform microarray analysis on each of 6 patients prior to inoculation and at 3 post-baseline timepoints. Our main analysis will identify differentially expressed genes between influenza and RSV at each post-baseline timepoint. The sample size, calculated using the size package from bioconductor which provides pilot data of gene expression variability from the U95 package, predicts that 6 individuals in each group will give us 80% power to detect a potential fold change of 3 in up to 67% of the genes with a Bonferroni multiple testing correction with a genome-wide 5% significance level.

Quantitative assessments of symptom scores, lung function, virus load, leukocyte numbers and inflammatory markers will be compared within subjects to determine differences between baseline and during infection. Intra-subject differences will be analysed using ANOVA and 2-tailed paired Student's t-tests or Wilcoxon signed rank test as appropriate. Correlations between inflammatory cell, illness severity, viral load and leukocyte counts will be examined using Spearman's rank correlations to investigate possible causal relationships.

Data and all appropriate documentation will be stored for a minimum of 10 years after the completion of the study, including the follow-up period according to Imperial College London policy.

REGULATORY ISSUES

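### The nasal scrape precedes nasosorption and lavage but is done only on some days, so change from baseline in nasal mediators is confounded with scrape status

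*Combined protocol and SAP*

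**What the plan says.** Section 1.13 places nasal sampling before bronchoscopy and adds that "All nasal procedures will be performed in the order below". The subsections that follow are 1.13.1 scrape, 1.13.2 nasosorption and 1.13.3 lavage.

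- Scrape (1.13.1): "Rhinopro® curettes will be used to obtain a sample of nasal epithelial cells from each nostril", which leaves no unscraped nostril as a control. The text adds that "the subject should not find this procedure painful, although a nasolacrimal reaction usually occurs".
- Nasosorption (1.13.2): absorptive strips are used "to obtain repeated samples of neat nasal ELF".
- Lavage (1.13.3): "Lavage fluid will later be analysed to quantify the degree of RSV or influenza shedding".
- Schedule (Tables 1 and 2): nasosorption and lavage are marked on each of days 1 to 10 and on days 14 and 28. The scrape is marked on only some of those days.
- Analysis (Statistics and Data Analysis): virus load and inflammatory markers, among other measures, "will be compared within subjects to determine differences between baseline and during infection". No term, restriction or sensitivity analysis for the scrape is described. The only procedure effect the plan adjusts for is that of bronchoscopy on symptoms (section 1.18).

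**The concern.** The plan itself expects a fluid reaction to the scrape and then, as the next step in the same nostril, collects what should be undiluted lining fluid. If a scrape preceded every sample, any effect would be roughly constant and would largely cancel in a within-subject comparison. It does not precede every sample. The baseline nasosorption samples are taken after a scrape, and most of the post-inoculation ones are not.

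A change in a nasal mediator from baseline to day 4, 5 or 6 therefore mixes two things: infection, and the removal of a preceding scrape. The switches between days 3 and 4 and between days 6 and 7 fall inside the day 2 to 7 window that section 1.18 treats as the period of maximal illness. A step in the mediator curve at those points could be biology or sampling. The plan applies the relevant principle elsewhere: nasal samples come before bronchoscopy to avoid contamination, and symptoms are recorded before procedures. It gives no reason for scraping first.

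**Working it through.** **Step 1. Schedule, first challenge (Tables 1 and 2, columns counted from the left).**

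| Day | Nasosorption | Lavage | Scrape the same day |
|---|---|---|---|
| Screening | yes | yes | yes |
| -14 | yes | yes | yes |
| 0 | no | yes | no |
| 1, 2, 3 | yes | yes | yes |
| 4, 5, 6 | yes | yes | no |
| 7 | yes | yes | yes |
| 8, 9 | yes | yes | no |
| 10 | yes | yes | yes |
| 14, 28 | yes | yes | no |

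Post-inoculation nasosorption days: 10 + 2 = 12. With a scrape: 5 (days 1, 2, 3, 7, 10). Without: 12 − 5 = 7 (days 4, 5, 6, 8, 9, 14, 28). Both pre-inoculation nasosorption samples are after a scrape. Lavage has the same split after inoculation, but also a scrape-free pre-inoculation sample on day 0, which section 1.10.2 confirms.

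In the second challenge, every nasosorption day from day 168 on (168, 178, 182, 196) carries a scrape, so the mismatch for mediators is confined to the first challenge.

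**Step 2. Can the analysis remove it?** Every participant has the same scrape status on a given day. The scrape indicator is therefore the sum of the indicators for the scraped days and is exactly collinear with day effects. With 16 participants per arm (the plan's sample size), two arms, and subject, day and arm-by-day terms:

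- Nasosorption, 13 days (-14, 1 to 10, 14, 28): 32 + 12 + 12 = 56 columns, rank 56. Adding the scrape indicator gives 57 columns and rank still 56.
- Lavage, 14 days (the same plus day 0): 32 + 13 + 13 = 58 columns, rank 58. Adding the scrape indicator gives 59 columns and rank still 58.

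Separation would need an assumed shape for the time course. The data cannot supply it.

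**Step 3. What a scrape effect would do. This is an illustration on assumed values.** The documents give no figure. Suppose the scrape multiplies the reading by f, there is no true change, and the standard deviation (SD) of the paired log10 difference is 0.3 to 0.5. An unscraped day then reads 1/f times a scraped baseline. For a two-sided 5% paired t-test with n = 16, the non-centrality is |log10 f| / (SD/√16), on 15 degrees of freedom.

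| f | Apparent ratio 1/f | Non-centrality, SD 0.5 to 0.3 | False-positive rate |
|---|---|---|---|
| 0.9 | 1.11 | 0.37 to 0.61 | 6 to 9% |
| 0.8 | 1.25 | 0.78 to 1.29 | 11 to 23% |
| 0.7 | 1.43 | 1.24 to 2.07 | 21 to 49% |
| 0.5 | 2.0 | 2.41 to 4.01 | 62 to 96% |
| 1.25 | 0.80 | 0.78 to 1.29 | 11 to 23% |
| 2.0 | 0.5 | 2.41 to 4.01 | 62 to 96% |

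The rows with f below 1 represent dilution: 25 to 100% added fluid gives f = 1/1.25 = 0.80 to 1/2 = 0.50. The rows above 1 represent mediator release, which is equally open because section 1.13.1 says the harvest includes goblet and mast cells. With f = 1 the rate is 5%.

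**The case against.** Several points on the other side stand and set the limits of this one.

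- **Virus load.** A reader might infer that virus load lacks a clean baseline too. It does not: day 0 lavage is scrape-free and matches days 4, 5, 6, 8, 9, 14 and 28. Virus load before inoculation should also be nil, so a proportional scrape effect could not create a rise from it. What remains is the shape of the curve between scraped and unscraped days.
- **Size and direction.** A reader might infer a spurious 1.25- to 2-fold rise on every unscraped day. That range only inverts an assumed fluid volume. The documents describe the scrape as painless and superficial; the effect could be small, or could run the other way.
- **Between-virus comparison.** A reader might infer that the RSV-versus-influenza comparison is biased. The first-challenge schedule is common to both arms, so same-day contrasts cancel the effect unless it differs by virus. The primary objective and the sample size concern T cells, not nasal samples.
- **Daily scrapes.** Section 1.10.2 lists scrapes in a run of items that begins with the word daily. On that reading days 1 to 10 are uniform and the day 3 to 4 and day 6 to 7 switches vanish. Days 14 and 28 would still differ from the day -14 baseline. The text and Table 1 need reconciling.
- **Actual order.** Sections 1.13.2 and 1.13.3 refer to a sampling SOP that is not among the documents, and the lists in sections 1.10.1 and 1.10.2 name the procedures in other orders. Those lists need not be sequences; section 1.13 is the only text that prescribes one. The order in practice still has to be confirmed.
- **Table reading.** Table 1 as read from the PDF has a trailing unlabelled column, and the screening text (1.6.1) mentions no nasal sampling. Exact days carry that caution; the on/off pattern does not depend on it.

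Like-with-like comparisons do exist: day -14 with days 1, 2, 3, 7 and 10, and days 4 to 6 with days 14 and 28. The second pair has no pre-infection sample, so it does not give a change from baseline.

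**Conclusion.** The point holds for within-subject change from baseline in nasal mediators during the first challenge. Baseline nasosorption follows a scrape, 7 of 12 post-inoculation samples do not, and scrape status cannot be separated from free day effects. The amount and direction of bias are unknown. For lavage virus load the point is limited to the shape of the time course. The documents do not support extending it to same-day RSV-versus-influenza contrasts, unless the scrape acts differently under the two viruses, or to the primary T-cell objective.

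This rests on three assumptions: that section 1.13 is the order actually used, that Tables 1 and 2 are the operative schedule, and that a scrape can alter fluid sampled soon afterwards, which the plan's own description makes plausible but does not show. It affects supporting analyses and is worth acting on because prevention costs almost nothing, whereas analysis cannot repair it later.

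**What to change.** 1. Reorder section 1.13 and the sampling SOP so that nasosorption comes first, lavage second and the scrape last, at every visit and in both arms.
2. Reconcile section 1.10.2 with Table 1 on which days carry a scrape.
3. For participants already sampled in the current order, record the order used, flag scrape days, and compare the day -14 nasosorption baseline only with scrape days (1, 2, 3, 7, 10). This still assumes that the scrape effect is the same in infected and uninfected mucosa.

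No procedure, visit or staff time is added. The scrape would be taken from recently washed mucosa, so cell yield may be slightly lower. Carry-over from a scrape to the next day's samples (days 2, 3, 4 and 8) is not removed. If the order changes part-way through and the arms are unequally recruited at that point, order becomes partly tied to virus; the recorded order should then be allowed for in between-arm nasal comparisons.

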1.13.1. Nasal scrape using Rhinopro®

Rhinopro® curettes will be used to obtain a sample of nasal epithelial cells from each nostril. This is a painless procedure and will not require local anaesthetic. The following technique is used:

The subject should be sat comfortably, ideally with their head fixed, looking forward, while their chin rests on a support (if available)

Tear bag and remove the flexible plastic Rhinopro® without contaminating the scoop end

Place a speculum in the nose to keep the cavity open and employ good lighting

Under direct visual inspection, insert the cupped probe onto the surface of the mid-inferior portion of the inferior turbinate. Note: Avoid the anterior bulb.

The Rhinopro® should be 3cm up the nose; the floor of the nostril can be used to rest on

Have the cup of the Rhinopro® at the correct angle

Gently press the cupped tip on mucosal surface and move out and in of nostril 3mm up to 3 times

Note that this area has limited sensitivity and the subject should not find this procedure painful, although a nasolacrimal reaction usually occurs

The cell harvest is epithelial cells, goblet cells and mast cells. It does not contain deeper layers of the mucosa. The sample obtained should be placed immediately into a tube containing RNA Cell Protect® (Qiagen) or Trizol and frozen at -80°C for storage prior to analysis.

1.13.2. Nasosorption

Up to four strips of SAM will be used (2 per nostril, one after the other) for 2 minutes to obtain repeated samples of neat nasal ELF. This is a painless minimally invasive procedure that will not require any local anaesthetic. Following sampling, SAM will be placed in a 1mL microfuge spin filter tube containing 250µL of elution buffer (PBS/1% bovine serum albumin/0.05% azide/0.05% Triton®). Further details are given in the SOP Human Sampling Procedures for Challenge Study.

The SAM will be transported on ice to the laboratory.

1.13.3. Nasal Lavage

Nasal lavage is performed using the following technique:

- 5mL of 0.9% saline is introduced into each nostril using a syringe attached to a nasal olive with the subject sitting with the head tilted forward
- The saline is then washed in and out of the nose approximately 10 times by alternately withdrawing and advancing the plunger of the syringe while the subject maintains a tight seal between the nasal olive and the nostril; the aim is to recover ~80% of the saline from the nose
- The fluid is then aliquotted into sterile microfuge tubes and centrifuged for analysis of cells

Lavage fluid will later be analysed to quantify the degree of RSV or influenza shedding. Multiplex PCR will be performed on the pre-inoculation lavage and post-inoculation lavage collected during the study to exclude the presence of other respiratory viruses. Supernatants will be frozen and stored at -80°C. Further details are given in the SOP Human Sampling Procedures for Challenge Study.

